Secondary Objectives	
 1. To compare the change in dysmenorrhoea VAS score between PEA/PLD and placebo treatment at baseline and 4 months after laparoscopic surgery for endometriosis. 2. To compare the change in dyspareunia, dyschezia and persistent pelvic pain VAS score between PEA/PLD and placebo treatment at baseline and 4 months after laparoscopic surgery for endometriosis. 3. To compare the change in dysmenorrhoea, dyspareunia, dyschezia and persistent pelvic pain VAS score between PEA/PLD and placebo, before surgery, in patients without surgical evidence of endometriosis. 4. To compare the change in dysmenorrhoea , dyspareunia, dyschezia and persistent pelvic pain VAS score between PEA/PLD and placebo, before surgery, and 4 months after laparoscopic surgery without evidence of endometriosis. 5. To compare the change of quality of life between PEA/PLD and placebo treatment in women with surgical evidence of endometriosis, before and after surgery. 6. To compare changes in cellular and molecular markers from endometriotic lesions, blood and peritoneal fluid samples between patients treated by PEA/PLD and placebo. 7. To correlate changes in VAS score with changes in cellular and molecular markers, in patients with endometriosis, treated by PEA/PLD and placebo. 8. To assess the side effects of PEA/PLD.
Inclusion Criteria:	
 • Women aged 18 - 45 with pelvic pain scheduled for laparoscopic treatment of possible endometriosis. Both women with and without previous evidence of endometriosis on ultrasound or previous surgery are eligible. • Women who agree to use any type of contraception and avoid conceiving during the 8-week treatment phase. • English speakers
Exclusion Criteria:	
 • Pregnancy or actively trying to conceive • Breastfeeding • Previous hysterectomy • Suspected malignancy • Inability to provide informed consent
Number of Planned Subjects:	130 patients in each arm, 260 in total
Investigational product:	palmitoylethanolamide/ polydatin 400 mg/40 mg
S a f e t y considerations:	Worldwide, more than 800,000 patients have been treated with PEA for various chronic pain conditions. No serious side effects have been reported (36)

Study Name: Palmitoylethanolamide and polydatin effect on pain and dysmenorrhea in women scheduled for laparoscopic treatment of possible endometriosis: a double blind randomised controlled trial

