5.1. Study Type & Design & Schedule

STUDY TYPE

Multi-centre prospective double-blind placebo-controlled randomized trial

METHODS

Patients will be identified through the Gynaecology 2 Unit outpatient clinic at the RWH, the Endosurgery Gynaecology clinics at the Mercy hospital for women, and associated private practices in Victoria. Referrals and patient histories will be screened by a specialist gynaecologist, fellow trainee or research assistant prior to clinic to identify potential participants. The study will be explained to potential participants. Patients who give their consent will be blindly randomized to receive either PEA/PLD 400 mg/40 mg or placebo. Following randomization, all participants will be asked to complete a NECST questionnaire including a set of pain VAS scales, Quality of life tool (see details in Study methodology). The same questionnaire, with additional questions regarding adverse side effects and treatment compliance, will then be filled 8 weeks later (still before surgery), and 4 months' after surgery. The questionnaire will be available online and as hard copy.

Surgery will then take place as planned with surgical samples for immunohistochemistry and RNA taken only from the Royal Women's Hospital recruited patients. Samples will be collected as described in "Study methodology".

A total number of 260 patients will be recruited, 130 in each arm.

STUDY TABLE

Study Name: Palmitoylethanolamide and polydatin effect on pain and dysmenorrhea in women scheduled for laparoscopic treatment of possible endometriosis: a double blind randomised controlled trial

Protocol Number: 1 Version 0.5, dated 29 September 2020

Assessment/Procedure	Recruitment	After 8 weeks of treatment (pre surgery)	day of surgery	4 months' After surgery
Informed Consent	x			
Baseline Questionnaire	x			
Follow up questionnaire		x		x
Laparoscopy tissue collection (endometrium, endometriosis, blood and peritoneal fluids at RWH only) and Surgeon report			x	

Study Name: Palmitoylethanolamide and polydatin effect on pain and dysmenorrhea in women scheduled for laparoscopic treatment of possible endometriosis: a double blind randomised controlled trial

Protocol Number: 1 Version 0.5, dated 29 September 2020

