6.2. Inclusion Criteria

- 6.2.1. women aged 18 - 45 with pelvic pain scheduled for laparoscopic treatment of possible endometriosis. Both women with and without previous evidence of endometriosis on ultrasound or previous surgery are eligible
- 6.2.2. women who agree to use any type of contraception and avoid conceiving during the 8-week treatment phase.
- 6.2.3. English speakers

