6.3. Exclusion Criteria

- 6.3.1. Pregnancy or actively trying to conceive
- 6.3.2. Breastfeeding
- 6.3.3. Previous hysterectomy
- 6.3.4. Suspected malignancy
- 6.3.5. Inability to provide informed consent

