7.1. Risk Management and Safety

Safety of PEA/PLD

The tolerability of the drug was viewed in a meta-analysis of all randomized, controlled trials involving the effect of PEA on pain score of different chronic pain conditions (34). Adverse events reported with PEA treatment in 786 patients included gastrointestinal upset (2), drowsiness (1), and heart palpitations (1).

No significant adverse side effects were reported in other studies. Moreover, treatment was given to patients seeking fertility, after surgical diagnosis of endometriosis while trying to conceive with no concern of teratogenicity (35).

Worldwide, more than 800,000 patients have been treated with PEA, most of them in Italy and Spain, with some in The Netherlands, Germany, UK, Canada and the US, and no serious side effects have been reported (36)

Treatment adverse reactions will be tracked by questionnaire. In case of any adverse reaction, patient can stop treatment at any time and seek advice with the allocated contact person for complaints in each hospital or 24 hours a day at the emergency department of each hospital for severe reactions.

Study Name: Palmitoylethanolamide and polydatin effect on pain and dysmenorrhea in women scheduled for laparoscopic treatment of possible endometriosis: a double blind randomised controlled trial

Protocol Number: 1 Version 0.5, dated 29 September 2020

As the PEA/PLD supplement has not yet been definitively proven to be non-teratogenic, patients participating in the study will be requested to avoid conceiving until after treatment and surgery. Participants not using contraception will be required to undergo a pregnancy test prior to commencing the research project.

We recognize that the study treatment and questionnaires may cause distress for some participants. Therefore, we have in place the following actions:

1. In the Patient Information and Consent Form (PICF) participants will be directed to contact a member of the research team (see list below of sites and contact persons) if they identify that they are experiencing distress as a result of participation in the study. The contact for Lifeline is also provided in this document.

Site	Contact Person
Epworth Hospitals	Gynaecology 2 Unit Fellow (RWH)
Mercy Hospital for Women (MHW)	Endosurgery Fellow
Royal Women's Hospital (RWH)	Gynaecology 2 Unit Fellow
Frances Perry House	Gynaecology 2 Unit Fellow (RWH)
Cabrini Malvern	[name]
Holmesglen Private	[name]
St Vincent's Private	[name]

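### The pregnancy test in Section 7.1 skips every woman using contraception, although Section 6.2.2 accepts any method, however unreliable

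*Protocol*

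**What the plan says.** Four statements in the protocol bear on this.

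- Section 6.3.1 excludes "Pregnancy or actively trying to conceive". The exclusion carries no qualification about contraceptive use.
- Section 6.2.2 admits "women who agree to use any type of contraception and avoid conceiving during the 8-week treatment phase". The synopsis repeats this criterion. Neither place says which methods count as reliable.
- Section 7.1 gives the reason for caution, namely that "the PEA/PLD supplement has not yet been definitively proven to be non-teratogenic".
- Section 7.1 then states the test: "Participants not using contraception will be required to undergo a pregnancy test prior to commencing the research project".

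The study table in Section 5.1, the procedures table in Section 5.2 and the methodology in Section 5.4 list no other pregnancy test.

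**The concern.** Whether a woman is tested depends on whether she uses contraception, and any method counts. Current use of a weak method is poor evidence that she is not already pregnant. The same is true of a method taken up only on joining the trial. For these women the protocol offers no objective check of its own exclusion criterion.

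What is at stake is the safety of a woman with an early, unrecognised pregnancy who starts a twice-daily product for which the protocol says teratogenicity has not been ruled out. A woman who knows that she is pregnant should be caught by the exclusion itself, so the gap concerns only pregnancies not yet recognised. The point is about participant safety and how eligibility is verified, not about inference.

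**Working it through.** The plan gives no figure to reproduce here, so the check is mainly a reading of the sections side by side.

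**Step 1: who is excluded and who is tested.**

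| Woman at entry | Excluded if pregnant (6.3.1) | Meets 6.2.2 | Tested (7.1) |
|---|---|---|---|
| Not using contraception, agrees to start | Yes | Yes | Yes |
| Using an unreliable method | Yes | Yes | No |
| Using a reliable method | Yes | Yes | No |

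The second row is the gap. Section 6.2.2 makes agreement to use contraception a condition of entry, so the untreated group in Section 7.1 makes sense only as a woman's status on entry. A woman who begins a method shortly beforehand could be placed in either the first or the second row.

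**Step 2: what else could detect a pregnancy before the first capsule.** Section 5.1 says "Referrals and patient histories will be screened by a specialist gynaecologist, fellow trainee or research assistant prior to clinic to identify potential participants". Section 5.4 adds a questionnaire that covers medical background. Both rely on what is already known or recorded, and neither is a test. Under Section 5.3 the pharmacy supplies capsules straight to the patient, and no pregnancy check is attached to that step. Any test on the day of surgery would come after the course has ended.

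**Step 3: exposure of one missed woman.**
- Inputs: twice-daily dosing for 8 weeks (Section 5.4); 130 women per arm, 260 in total (Section 5.1).
- Scheduled doses: 2 × 56 = 112. This is an upper limit, because the course would stop if the pregnancy were noticed.
- Chance that she is allocated active product: 130/260 = 0.5.
- Average scheduled active doses per missed woman: 0.5 × 112 = 56.

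**Step 4: number of missed women.** This would be the number enrolled, times the share using an unreliable method, times the share of those with an unrecognised pregnancy. The protocol gives the first (260) and neither of the others, so no count is offered.

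**Step 5: cost of testing everyone.** 2 × 130 = 260 tests at the planned size. Section 7.3 allows recruitment to continue until the target per group is met, so the total could be higher. How much higher depends on how that section is read.

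**The case against.** The strongest reply is that the rule is coherent and based on risk. Section 6.3.1 sets a condition, and Section 7.1 decides whose status needs checking; it picks the women most likely to be pregnant. Other exclusions, such as breastfeeding, have no stated test either. This stands against any claim that the two sections conflict. A reader might infer a contradiction, but excluding all pregnant women while testing only some is not inconsistent. What it leaves unanswered is that no reliability standard separates the untested women from the tested ones.

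A second reply is that the harm is small. Half of the women receive placebo. Section 3.2 describes both ingredients as over-the-counter food supplements. Section 7.1 reports use in women "while trying to conceive with no concern of teratogenicity". Section 7.2 removes any woman who becomes pregnant during treatment. All of this stands and lowers the weight of the point. The safeguard in Section 7.2 does, however, depend on the pregnancy being noticed, and no test during treatment is stated.

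A third reply concerns logistics. Recruitment and consent can run by phone (Sections 6.1 and 6.4), and capsules go directly to patients. But Section 7.1 already requires a test from some women before they start, so a route for obtaining one must exist.

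Finally, a reader might see a second conflict. Section 6.2.2 covers the 8-week treatment phase, whereas Section 7.1 says "patients participating in the study will be requested to avoid conceiving until after treatment and surgery". With surgery within 2 weeks of finishing treatment (Section 5.4), that is 56 days against 56 to 70 days. A woman who follows Section 7.1 satisfies both, and the extra 0 to 14 days fall after the last capsule. The documents do not support calling this a conflict.

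**Conclusion.** The point holds as a cheap safety improvement. In the visible text, a woman using an unreliable method can start the course with no objective check of exclusion 6.3.1.

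The conclusion rests on two conditions. First, no wider test is stated in material not shown: the consent pages and Figure 1 are missing, and a test described only there cannot be ruled out. Second, Section 7.1 is applied as worded, so that use of any method removes the test.

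It would go too far to infer that pregnant women will be dosed in some known number, that a teratogenic hazard has been shown, or that the trial's results are at risk. The protocol gives no rates from which to count cases. It reports an absence of proof of safety, not a signal of harm. Sample size, error rates and the primary analysis do not depend on this rule.

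**What to change.** In Section 7.1, require a negative urine pregnancy test before the first capsule for all participants. At minimum, require it for every woman not on a reliable method, and name the methods that qualify. Use the route already needed for the women whom Section 7.1 tests, and have the result confirmed before the pharmacy releases the capsules.

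The cost is one wording change, about one inexpensive urine test per participant, and one added check before release across the sites. The narrower option needs fewer tests but requires a list of accepted methods and a record of each woman's method at entry.

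Bringing the avoidance period in Section 6.2.2 and the synopsis into line with Section 7.1 is optional tidying that could go into the same amendment.

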7.2. Handling of Withdrawals

Should a participant choose to withdraw from the study no further information will be collected. If the participant withdraws prior completing 6 weeks of medical treatment, she will be removed from the study.

If the participant withdraws following the medical treatment and the second questionnaire but either prior to or after surgery, she will be asked if the data collected prior to their withdrawal is able to be used. Should they decline the data will be removed from the data bank and stored in a separate folder to ensure it is not included in the final analysis.

If the participant falls pregnant during the medical treatment phase, she will be removed from the study.

If the participant falls pregnant after the medical treatment phase and the surgery but prior the last questionnaire she will remain in the study and complete the last questionnaire as planned.

If participants have consumed less than 80% of the treatment, they will be removed from the study.

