4.3. Outcome Measures

Primary outcomes

- 4.3.1. To compare the change in dysmenorrhoea VAS score between PEA/PLD and placebo treatment in patients with endometriosis prior to laparoscopic surgical treatment.
- 4.3.2. To compare the change in dyspareunia, dyschezia and persistent pelvic pain VAS score between PEA/PLD and placebo treatment in patients with endometriosis prior to laparoscopic surgical treatment.

Secondary outcomes

- 4.3.3. To compare the change in dysmenorrhoea VAS score between PEA/PLD and placebo treatment at baseline and 4 months after laparoscopic surgery for endometriosis.
- 4.3.4. To compare the change in dyspareunia, dyschezia and persistent pelvic pain VAS score between PEA/PLD and placebo treatment at baseline and 4 months after laparoscopic surgery for endometriosis.

Study Name: Palmitoylethanolamide and polydatin effect on pain and dysmenorrhea in women scheduled for laparoscopic treatment of possible endometriosis: a double blind randomised controlled trial

Protocol Number: 1 Version 0.5, dated 29 September 2020

- 4.3.5. To compare the change in dysmenorrhoea, dyspareunia, dyschezia and persistent pelvic pain VAS score between PEA/PLD and placebo, before surgery, in patients without surgical evidence of endometriosis.
- 4.3.6. To compare the change in dysmenorrhoea, dyspareunia, dyschezia and persistent pelvic pain VAS score between PEA/PLD and placebo, at baseline and 4 months after laparoscopic surgery without evidence of endometriosis.
- 4.3.7. To compare the change of quality of life between PEA/PLD and placebo treatment in women with surgical evidence of endometriosis, before surgery and again after surgery.
- 4.3.8. To compare changes in cellular and molecular markers from endometriotic lesions, blood and peritoneal fluid samples between patients treated by PEA/PLD and placebo.
- 4.3.9. To correlate changes in VAS score with changes in cellular and molecular markers, in patients with endometriosis, treated by PEA/PLD and placebo.
- 4.3.10. To assess the side effects of PEA/PLD.

5. Study Design

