5.4. Study methodology

All subjects will be given oral and written information about the study and informed written consent will be obtained by our Research Nurses / Assistant (see attached patient information and consent forms). After consent has been obtained, an initial questionnaire will be completed by the women. The questionnaire includes demographic details, medical background, pain questions about menstrual pain and other pelvic pain symptoms including dysmenorrhoea, deep dyspareunia, dyschesia, daily pain and quality of life assessment.

Quality of life domains will include physical and mental health.

Recruited patients will then be blindly randomized to receive either PEA/PLD 400 mg/40 mg or placebo twice daily for 8 weeks.

Treatment will be prepared by a specialist compounding pharmacy in the form of similar capsules for PEA/PLD and placebo, distributed in similar containers with their content only known to the pharmacists.

The same questionnaire (without the demographic and medical history part) will then be filled at the end of 8 weeks of treatment (still before surgery) with additional adverse drug side effects and treatment compliance assessment.

Surgery will take place within 2 weeks of finishing the study treatment.

Final questionnaire will be sent to participants 4 months' after the surgery to evaluate pain and quality of life.

Collection of tissue Samples and clinical/medical Information

Only patients operated on at the Royal Women's Hospital will be consented for tissue/ biofluid collection. Patients operated at the Mercy Hospital for Women or private hospitals will have their surgeries as planned without any other surgical intervention.

Blood: During surgery, blood samples (25-50 mls, or 1¼ -2½ tablespoons) will be drawn and processed in the laboratories at the RWH.

Endometrial Biopsy: A routine endometrial biopsy will be collected from each woman. The biopsy will be collected following collection of a clinical biopsy during hysteroscopy (endometrial biopsies will only be collected from women providing clinical consent for an endometrial biopsy as part of her planned medical procedure). Endometrial samples will be histologically assessed for cycle stage and some will be stored in RNA later (Life Technologies) for mRNA (NGS analysis) or protein expression studies or used immediately in in vitro cell culture studies.

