7.3. Replacements

We will continue to recruit until we have 130 participants per group for the primary outcome. Any withdrawals after this point will not be replaced because this data is for secondary outcomes only.

8. Statistical Methods

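### Section 7.2 lets a woman who withdraws after week 8 have her primary pain scores left out of the analysis, a loss that 7.3 assumes cannot happen

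*Protocol*

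**What the plan says.** Protocol 4.3 gives the first primary outcome as "To compare the change in dysmenorrhoea VAS score between PEA/PLD and placebo treatment in patients with endometriosis prior to laparoscopic surgical treatment". Section 5.4 places the second questionnaire at the end of the 8 weeks of treatment, before surgery, so baseline and week 8 supply the two VAS values of the primary change score. Endometriosis is confirmed or excluded only at surgery (3.1).

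Section 7.2 opens its withdrawal rules with "Should a participant choose to withdraw from the study no further information will be collected". On late withdrawal it says: "If the participant withdraws following the medical treatment and the second questionnaire but either prior to or after surgery, she will be asked" whether the data gathered so far may be used. If the answer is no: "Should they decline the data will be removed from the data bank and stored in a separate folder". The stated purpose is "to ensure it is not included in the final analysis". The rule makes no exception for the primary scores.

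Section 7.3 sets the recruitment target: "We will continue to recruit until we have 130 participants per group for the primary outcome". It then says: "Any withdrawals after this point will not be replaced because this data is for secondary outcomes only".

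**The concern.** There are two problems.

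The first is when the choice is made. The woman is asked after she knows how her pain changed, whether she had side effects and, if she has been operated on, what was found. Whether her scores stay in the analysis can therefore depend on those scores or on things related to them. Everything collected before withdrawal is excluded, baseline included. The linear models in 8.2, which adjust for pre-treatment pain, would then have nothing from her to condition on.

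The second is a contradiction. Section 7.3 treats the primary data as secure once 130 per group have been reached, and it declines to replace later withdrawals for that reason. Section 7.2 allows one of those later withdrawals to take primary data out. A woman can count toward the 130, withdraw after surgery, decline, and leave the primary analysis without being replaced.

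This is not a detail left to an analysis plan. The protocol fixes the rule, and an analysis plan cannot restore data that the protocol has excluded.

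**Working it through.** **1. What exists when she is asked (4.3, 5.4, 7.2)**

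| Time of withdrawal | Both VAS values | Endometriosis status | Primary result |
|---|---|---|---|
| After week 8, before surgery | yes | no; nothing more is collected | scores complete, membership of the primary population unknown |
| After surgery | yes | yes | complete |

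In the first row she may be unusable for the primary analysis even if she agrees. The loss of a complete primary result is therefore confined to the second row.

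**2. Sections 7.2 and 7.3 side by side**

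7.3: after the target is met, withdrawals cost secondary data only, so there is no replacement. 7.2: a withdrawal after the second questionnaire, including after surgery, can remove all data collected. Both cannot hold for a woman who declines. This step needs no assumed figure.

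**3. The plan's own sample size (8.1)**

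Inputs: difference 1 point, SD 2 (d = 1/2 = 0.5), two-sided alpha 0.05, power 0.80. A two-sample t-test needs 63.8, so 64 per group, as stated. Inflation for 30% drop-out and 30% without endometriosis: 64 / (0.7 × 0.7) = 130.6, against the stated 130. The figures reproduce.

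Section 8.1 words this calculation for the change to 4 months after surgery. I assume the same difference and SD for the week-8 change.

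**4. Possible shift in an arm's mean**

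The protocol gives no refusal rate. Let f be the share of an arm's evaluable women who are removed and d* the difference in mean change between those removed and those kept. The mean of those kept differs from the mean of all by f × d*. With d* = 2 points (assumed) and removal in one arm only (assumed):

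- f = 2%: 0.02 × 2 = 0.04 point
- f = 5%: 0.05 × 2 = 0.10 point
- f = 10%: 0.10 × 2 = 0.20 point

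The treatment difference moves by the difference between the two arms' shifts. If both arms lose the same share with the same d*, the shifts cancel.

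**5. Power**

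Two-sample t-test, d = 0.5, n × (1 − f) per arm in both arms, for two starting points:

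- 130 per arm reach week 8, as 7.3 states, counted before surgical confirmation: 130 × 0.7 = 91 with endometriosis.
- The 30% drop-out allowance is already used up: 130 × 0.7 × 0.7 = 63.7.

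| f | n from 91 | power | n from 63.7 | power |
|---|---|---|---|---|
| 0 | 91.0 | 0.918 | 63.7 | 0.800 |
| 2% | 89.2 | 0.913 | 62.4 | 0.791 |
| 5% | 86.5 | 0.905 | 60.5 | 0.779 |
| 10% | 81.9 | 0.889 | 57.3 | 0.756 |

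**The case against.** The strongest defence is that this is a consent provision. The trial does not discard data of its own accord. It asks, and it excludes only on an explicit refusal; the separate folder is how that refusal is carried out. The consent form is not at hand, so what women are told at entry cannot be judged. This stands, and it is why the remedy cannot be to override a refusal.

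Blinding also limits the problem. Participants, medical staff, surgeons and investigators do not know the allocation (5.3, 5.4), so refusal cannot follow known treatment. It can still follow perceived benefit or side effects, and through them it could differ by arm.

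The event needs two steps: leaving after completing treatment and questionnaire, then refusing use of data already given. Nothing in the protocol points to a rate as high as 5% or 10%. The automatic removals in 7.2 (withdrawal before 6 weeks, under 80% of treatment taken, pregnancy during treatment) need no refusal and may well cost more.

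A reader might infer that the rule breaks the randomised comparison. The text shows only that removal could depend on outcome, not that it will. A reader might also infer a clear loss of power, from 0.80 to 0.78 or 0.76. That holds only if the drop-out allowance is already spent, and 8.1 does not restrict the allowance to early drop-out, so late refusals may already be within it. If 130 per arm reach week 8, power stays well above the planned 0.80.

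**Conclusion.** The point holds, with moderate weight. Section 7.2 allows primary scores to be taken out of the analysis by a choice made after the woman knows her result, and 7.3 rests on the premise that this cannot occur. The contradiction is certain from the text. Selective loss is a possibility whose size the protocol does not let one estimate.

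Under the assumed one-arm, 2-point illustration, the shift runs from 4% to 20% of the one-point target for removal shares of 2% to 10%. It would be smaller, or nil, if removal were similar in both arms. Loss of power is a minor consideration. The case for change rests on the contradiction and on the possibility of outcome-related removal, together with the low cost of preventing both.

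**What to change.** Subject to ethics approval, state in 7.2 and in the consent form, before entry, that withdrawal ends all further contact and data collection, and that coded data collected up to that day are kept and analysed. This replaces the routine question at withdrawal.

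If an opt-out must remain, honour it and make two changes. In 7.3, say that women whose primary data are removed do not count toward the 130 per group, and drop the premise that later withdrawals affect secondary outcomes only. Also commit to reporting the number of such removals by arm.

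The cost is a short amendment to the protocol and the consent form, with ethics review. The downside is that women lose a routine offer to have past data left out. If the opt-out stays, some replacement recruitment may be needed, probably little.

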The tolerability of the PEA was reviewed in the above meta-analysis (34). Adverse events reported from PEA treatment to 786 patients included only gastrointestinal upset (2), drowsiness (1), and heart palpitations (1). No significant adverse side effects were reported in other studies. Moreover, treatment was given to patients seeking fertility, after surgical diagnosis of endometriosis while trying to conceive with no concern of teratogenicity (35).

Worldwide, more than 800,000 patients have been treated with PEA, most of them in Italy and Spain, with some in The Netherlands, Germany, UK, Canada and the US, and no serious side effects that have been reported (36).

Polydatin or its origin Reserveol, are widely used in humans because of their reported potential antitumor and anti-inflammatory properties (37). Despite the extensive research on the benefits derived from Reserveol, there was not enough research conducted to assess its harmful effects. In high doses of Reserveol (2-5 g per day) can lead to episodes of light and mild diarrhea, nausea, hypersensitivity and anal pruritus.

It appears that Reserveol needs to be administered in extremely high doses for it to elicit a significant toxic effect in vivo. It is generally well tolerated, some adverse effects including nephrotoxicity and gastrointestinal problems were reported in human subjects taking high dose (more than 1000 mg/day) (38, 39). A 450 mg/day dose of Reserveol was reported to be a safe dose for a 60-kg person (40). Overall, Reserveol is well tolerated in healthy individuals.

Interestingly, Di Paola R. et al, (41) suggested that PEA/PLD may be of use to inhibit development of endometriotic lesions in rats. In the treated group (N=10), a smaller endometriosis lesion diameter was found (as compared to controls), with improved fibrosis score and mast cell number decrease. PEA/PLD administration also decreased angiogenesis (vascular endothelial growth factor), nerve growth factor, intercellular adhesion molecule, matrix metalloproteinase 9 expression, and lymphocyte accumulation. It also reduced peroxynitrite formation, (poly-ADP) ribose polymerase activation, I κ B alpha phosphorylation and nuclear factor- κ B translocation to the nucleus.

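### Section 7.2 removes women who conceive during treatment, and nothing in the protocol keeps a product-exposed pregnancy in safety data collection

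*Protocol*

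**What the plan says.** Section 7.1 (Risk Management and Safety) asks participants to avoid conceiving until treatment and surgery are over. The reason begins: "As the PEA/PLD supplement has not yet been definitively proven to be non-teratogenic". The same section cites an earlier study, in women seeking pregnancy, as having raised no such worry.

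Section 7.2 (Handling of Withdrawals) sets two rules by time of conception:
- During treatment: "If the participant falls pregnant during the medical treatment phase, she will be removed from the study".
- Later: "If the participant falls pregnant after the medical treatment phase and the surgery but prior the last questionnaire she will remain in the study". What she then does is finish the final questionnaire.

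Sections 5.1 and 5.4 fix when safety information is gathered. Side-effect and compliance questions are added to the 8-week questionnaire. Section 5.4 describes the final questionnaire, 4 months after surgery, as covering pain and quality of life. Section 5.1 can be read as repeating the side-effect questions then. The study table in 5.1 lists consent, questionnaires, tissue collection and the surgeon's report, and nothing on pregnancy. Outcome 4.3.10 is "To assess the side effects of PEA/PLD".

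**The concern.** The protocol names a possible harm to a pregnancy and then, for a woman who conceives while taking capsules, provides only for her removal. If removal means that data collection stops, two kinds of information go with her: the course and outcome of a pregnancy exposed to the product, and her ordinary side-effect answers, which are first asked at 8 weeks. Both belong to 4.3.10. The trial could then report no pregnancy-related harm because it held no record of the pregnancies concerned.

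Who stays under safety observation after exposure is decided in the protocol. A statistical analysis plan cannot recover data that were never collected. The point is separate from whether such women enter the pain analysis.

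**Working it through.** **1. The rules set side by side**

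| Time of conception | Rule in 7.2 | Pregnancy outcome recorded? |
|---|---|---|
| First to last capsule (8 weeks) | Removed | No provision found |
| Last capsule to surgery (0 to 2 weeks, section 5.4) | None | No provision found |
| After surgery, before the final questionnaire | Retained | No provision found |

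The middle row is a gap in the rule itself. Section 7.1 asks women to avoid conceiving until after surgery, so it covers a period for which 7.2 gives no instruction.

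**2. How many pregnancies on active product**

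The protocol gives no expected number, so there is no figure of its own to reproduce. Inputs: 130 women per arm (section 8.1), 8 weeks of treatment (section 5.4), and an assumed 2 to 15 pregnancies per 100 woman-years. The rate is an assumption and is not in the documents.

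- Exposure on active product: 130 × 8/52 = 20 woman-years.
- Expected pregnancies: 20 × 0.02 = 0.4, to 20 × 0.15 = 3.0.
- Chance of at least one, taking a Poisson count: 1 − e^(−0.4) = 0.33, to 1 − e^(−3) = 0.95.
- Adding the longest gap before surgery: 130 × 10/52 = 25 woman-years, giving 0.5 to 3.75.

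The 20 woman-years assume that all 130 women take the full course. Early stopping lowers the figure. Replacement under section 7.3, which continues recruitment to 130 per group for the primary outcome, raises it.

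**3. Whether the present schedule could reach a birth outcome**

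- Four months is 4 × 365.25/12/7 = 17.4 weeks.
- The final questionnaire therefore falls 8 + 0 + 17.4 = 25.4 to 8 + 2 + 17.4 = 27.4 weeks after the first capsule.
- Assuming birth about 38 weeks after conception (not in the documents), a pregnancy conceived on the first treatment day is still at least 38 − 27.4 = 10.6 weeks from term at the last contact.

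So retaining these women to the existing last questionnaire would not be enough.

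**4. What the outcomes could show**

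With three exposed pregnancies and no harm in any, the one-sided 95% upper limit for the harm rate is 1 − 0.05^(1/3) = 0.63. The data would serve as a safety record and could not support a claim of safety.

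**The case against.** The strongest reply is that 7.2 decides who supplies pain data and says nothing about safety contact. The term for removal is undefined, and the same section applies it to women who took under 80% of treatment, where it reads as exclusion from the data set. The sentence "Should a participant choose to withdraw from the study no further information will be collected" is written for women who choose to leave. This stands: the end of data collection after removal for pregnancy is inferred. The inference is still the likely one, because no section gives these women any further contact.

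A second reply is that part of the evidence is out of sight. The consent pages and the questionnaire items are not shown, and participants also join the national registry described in 3.2, which holds health outcomes. This also stands, so one can say only that this protocol makes no provision, not that exposed pregnancies would never be followed.

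A reader might infer several stronger things that the documents do not support:
- That follow-up runs opposite to risk, with exposed pregnancies dropped and unexposed ones observed. The retained woman "she will remain in the study and complete the last questionnaire as planned", and no pregnancy outcome is mentioned for her either.
- That retained pregnancies begin long after the last capsule. Surgery comes within 2 weeks of the end of treatment, so such a pregnancy may begin within days of the last capsule.
- That teratogenicity is the only risk left open. Of resveratrol, which section 3.2 links to polydatin, that section says "there was not enough research conducted to assess its harmful effects".
- That allocation would be lost. The dispensing pharmacy holds the randomisation lists (section 5.3).
- That 0.8 to 6 exposed pregnancies are expected. That count covers both arms (260 × 8/52 = 40 woman-years), and placebo women are not exposed to the product.

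Finally, contraception is required, women trying to conceive are excluded, and infertility is among the listed symptoms of the disease, so the true rate may lie near the low end of the range. That reduces the expected number without removing the case.

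**Conclusion.** The point holds in a limited form. Section 7.2 states a rule that takes a woman who conceives during treatment out of the study. It leaves up to 2 weeks before surgery without a rule, and no section records how any pregnancy ends. Followed literally, it would probably lose a product-exposed pregnancy and the woman's 8-week side-effect answers.

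The size is small: an expected 0.4 to 3 pregnancies on active product, with a chance between about one in three and 95% that at least one occurs. This rests on the assumed pregnancy rate and full-course exposure. No efficacy result depends on it. It merits a change because a declared uncertainty meets a rule that discards the relevant record, and because the change is cheap.

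**What to change.** Reword 7.2 to say what removal covers, separating removal from treatment or from the pain analysis from the end of safety data collection. State that a woman who conceives between first capsule and surgery stays, with her consent, in safety data collection:
- the side-effect questions;
- dates of first and last capsule;
- estimated date of conception;
- pregnancy outcome, with a contact later than the present final questionnaire.

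List these by arm under 4.3.10 once the trial is unblinded. Align the consent form if it does not already provide for this.

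The sponsor should also reconcile three passages. Section 6.2 requires agreement to contraception for the 8 treatment weeks. Section 7.1 extends the request to avoid conception through surgery and provides for participants who use no contraception. Section 7.2 is silent on the interval before surgery. Decisions on capsules and clinical care are for the sponsor and are not part of this change.

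The cost is protocol wording, possibly consent wording, and one later contact for a few women. Some outcomes will arrive during the planned 12 months of analysis and write-up.
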